For the selected secondary endpoints (percent change from baseline to Week 12 in non-HDL-C, apoB, TC, and hsCRP), the data will be analyzed in the similar fashion as for the primary endpoints and then the step-down procedure as detailed above will be applied to the analysis results for each treatment comparison of interest (BA 180 mg + EZE 10 mg FDC versus placebo; BA 180 mg + EZE 10 mg FDC versus BA 180 mg; BA 180 mg + EZE 10 mg FDC versus EZE 10 mg). Other secondary endpoints based on HDL-C and TG will be analyzed separately outside of the step-down procedure. For HDL-C, non-HDL-C, TG, and TC, baseline is defined as the mean of the values from Week -2 (Visit S1) and predose Day 1/Week 0 (Visit T1), while baseline for apoB and hs-CRP is the predose Day 1/Week 0 value.

Safety Analyses

The summarization of AEs will include only TEAEs, any unfavorable and unintended sign, symptom, or disease occurred or worsened in severity since the first dose of the IMP until 30 days after study completion whether or not related to the product. An SAE is defined as any untoward medical occurrence that occurs at any dose that results in death, is life-threatening, requires inpatient hospitalization, results in persistent or significant disability, or results in a congenital anomaly/birth defect. TEAEs and SAEs will be summarized by system organ class (SOC), severity, and relationship to study drug for each treatment group.

Clinical safety laboratories, including hematology, blood chemistry, HbA_{1C}, glucose, and urinalysis; PE findings; vital signs; ECG readings; and weight will be summarized by the value and by change from baseline in the value (where appropriate) at each post baseline time point.

TABLE OF CONTENTS

1.	TITLE PAGE.....	1
2.	SYNOPSIS	2
3.	LIST OF ABBREVIATIONS AND DEFINITIONS OF TERMS.....	18
4.	INTRODUCTION	22
4.1.	Cardiovascular Disease and LDL-C-Lowering Drugs	22
4.2.	Background on Bempedoic Acid.....	24
4.2.1.	Mechanism of Action	24
4.2.2.	Nonclinical Experience.....	24
4.2.3.	Previous Human Experience.....	25
4.2.4.	Dose Selection	26
4.3.	Background on Ezetimibe.....	26
4.4.	Risk Benefit Summary.....	26
5.	TRIAL OBJECTIVES AND PURPOSE.....	27
5.1.	Objectives	27
5.1.1.	Primary Objectives	27
5.1.2.	Secondary Objectives	27
5.1.3.	Exploratory Objective:.....	27
5.2.	Study Endpoints.....	27
5.2.1.	Primary Endpoint.....	27
5.2.2.	Secondary Endpoints	27
5.2.3.	Exploratory Endpoints.....	28
5.2.4.	Safety Endpoints.....	28
6.	INVESTIGATIONAL PLAN.....	29

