5.3.2 Secondary and Exploratory Efficacy Endpoint Analyses

Key secondary efficacy endpoints, which include the percent change from baseline to Week 12 in LDL-C, non-HDL-C, TC, and apoB, will be analyzed in a similar manner as the primary efficacy endpoint.

For hsCRP, a non-parametric (Wilcoxon rank-sum test) analysis with Hodges-Lehmann estimates and confidence interval will be performed because based on historical knowledge, publication precedence (Brendan etc., 2006) and recent data available, hsCRP is known to be skewed by extreme values and have non-normal distribution. HDL and TGs will be summarized using descriptive statistics for the observed value and the change/percent change from baseline at each protocol scheduled visits.

If co-primary endpoint family achieves statistical significance, a list of selected secondary endpoints will be tested in sequential order within each comparison group. The alpha allocation among the three comparison groups is: alpha = 0.01 for FDC vs. Placebo alpha = 0.02 for FDC vs. EZE; alpha = 0.02 for FDC vs. BA.

Missing values for these secondary endpoints will be imputed using multiple imputations method as described for primary endpoint. All other secondary endpoints not included in the step-down procedure (Figure 2) will be tested at significant level of 0.05 without multiplicity adjustment. Only observed data will be used for these analysis.

Other secondary endpoints of HDL-C and TGs will be summarized using descriptive statistics at week 12.

[figure not shown]
By-visit summary for all efficacy endpoints (LDL-C, non-HDL-C, TC, ApoB, hsCRP, HDL-C and TGs) using FAS and treatment completer set will be provided for both conventional and standard units.

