To answer the question and ensure the integrity of the data and related analysis and quality, we propose to conduct sensitivity analysis. The focus of the sensitivity analysis is to examine if the data issue impacts the efficacy and safety results of the trial. We will repeat selected key analyses after excluding all 81 patients from these 3 sites, [REDACTED] and [REDACTED]

After excluding patients from these 3 sites [REDACTED], we will provide tables for disposition and demographics. We will repeat the statistical analyses for:

1. The co-primary efficacy endpoints, which consist of three comparisons of the percent change from baseline to Week 12 in LDL-C: bempedoic acid-ezetimibe fixed dose combination (FDC) vs. placebo, FDC vs. ezetimibe, and FDC vs. bempedoic acid;
2. Key secondary efficacy endpoints which include the percent change from baseline to Week 12 in non-HDL-C, TC, apoB, and hsCRP;
3. Overview of treatment emergent adverse events; and
4. Laboratory parameter of interest including ALT and AST abnormalities. The clinical relevance and statistical significance for the results will be re-evaluated for the primary and key secondary endpoints.

The safety profile will also be reviewed during the sensitivity analysis. The list of tables for sensitivity analysis is provided in

Table 1.

Table 1. List of Tables for Study 1002FDC-053 Sensitivity Analysis.

T14.1.1.1	Patient Disposition
T14.1.2.1	Demographic and Baseline Characteristics - Safety Population
T14.1.2.2	Demographic and Baseline Characteristics - Full Analysis Set
T14.2.1.1.1	Primary Analysis: Percent Change from Baseline in Low-density Lipoprotein Cholesterol (LDL-C) at Week 12 (Multiple Imputation (MI)) Full Analysis Set
T14.2.1.1.3	Sensitivity Analysis: Percent Change from Baseline in Low-density Lipoprotein Cholesterol (LDL-C) at Week 12 (Observed Data) Treatment Completer Analysis Set
T14.2.1.2.1	Statistical Analysis of Percent Change from Baseline in High-sensitivity C-reactive Protein (hsCRP) at Week 12 via Non-parametric Approach (Observed Data) Full Analysis Set
T14.2.1.3.1	Statistical Analysis of Percent Change from Baseline in Non-High-density Lipoprotein Cholesterol (Non-HDL-C) at Week 12 (Multiple Imputation (MI)) Full Analysis Set
T14.2.1.4.1	Statistical Analysis of Percent Change from Baseline in Apolipoprotein B (apo-B) at Week 12 (Multiple Imputation (MI)) Full Analysis Set

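### The plan treats hs-CRP as a step-down endpoint but gives it no workable imputation rule, and the only table list shown runs it on observed data

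*SAP*

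**What the plan says.** **Membership of the step-down.** The Protocol Synopsis (Secondary Efficacy Analysis) begins "For the selected secondary endpoints (percent change from baseline to Week 12 in non-HDL-C, apoB, TC, and hsCRP" and says that "the step-down procedure as detailed above will be applied to the analysis results for each treatment comparison of interest". It places HDL-C and TG outside the procedure. The SAP Addendum of December 24, 2018 describes "Key secondary efficacy endpoints which include the percent change from baseline to Week 12 in non-HDL-C, TC, apoB, and hsCRP". The main SAP text differs. Section 5.3.2 reads "Key secondary efficacy endpoints, which include the percent change from baseline to Week 12 in LDL-C, non-HDL-C, TC, and apoB", without hs-CRP, and leaves the step-down list to Figure 2, whose content is not shown in the public text.

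**Missing data.** After introducing the sequential testing, SAP 5.3.2 states "Missing values for these secondary endpoints will be imputed using multiple imputations method as described for primary endpoint". It then turns to a different group: "All other secondary endpoints not included in the step-down procedure (Figure 2) will be tested at significant level of 0.05 without multiplicity adjustment". The sentence after that restricts those analyses to observed data.

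**Primary rule.** Under SAP 5.3.1, a patient with a missing value who is off treatment receives the baseline value. A patient with a missing value who is still on treatment is imputed by regression. About 200 datasets are analysed by ANCOVA and combined by Rubin's method.

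**hs-CRP method.** SAP 5.3.2: "For hsCRP, a non-parametric (Wilcoxon rank-sum test) analysis with Hodges-Lehmann estimates and confidence interval will be performed". The stated reason is skewness.

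**Table list.** In Table 1 of the same Addendum, the hs-CRP table (T14.2.1.2.1) is titled "at Week 12 via Non-parametric Approach (Observed Data) Full Analysis Set". The non-HDL-C, apoB and TC tables are labelled as multiple imputation. No imputed hs-CRP table is listed.

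**The concern.** If hs-CRP is in the step-down, its test uses alpha of 0.01 against placebo or 0.02 against each component and can support a multiplicity-controlled claim. Such a test needs one prespecified missing-data rule. The text points to multiple imputation, gives no way to carry it out for a rank test, and the table list points to observed data.

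The choice matters because of which patients lack hs-CRP. The note to Protocol Appendix 1 keeps patients who stop drug on the visit schedule but excepts apoB and hs-CRP from their laboratory tests. Missing hs-CRP would then fall mainly on patients whom the primary rule sets to no change. ApoB has the same sampling gap but is imputed in the table list.

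**Working it through.** **Step 1: the passages side by side.**

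| Question | Protocol Synopsis | SAP 5.3.2 | SAP Addendum |
|---|---|---|---|
| hs-CRP in the step-down? | Yes | Not readable (absent from key secondary sentence; Figure 2 not shown) | Called key secondary |
| Analysis | Similar to the primary | Wilcoxon/Hodges-Lehmann | Non-parametric |
| Missing data | Similar to the primary | MI for sequentially tested endpoints; observed data for the others | Observed data |

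The SAP supersedes the Protocol on analysis, so the Wilcoxon test replaces ANCOVA. That leaves the missing-data rule open.

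**Step 2: can the primary rule be applied as written?** SAP 5.3.1 pools least squares means and their standard errors. It does not say how Wilcoxon p-values or Hodges-Lehmann estimates are combined over 200 datasets, or on what scale a skewed variable is imputed.

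**Step 3: who is missing?** The Appendix 1 note exempts hs-CRP after drug withdrawal. Protocol 10.5.5 lists hs-CRP at Week 12/early termination, and Appendix 1 footnote 2 calls for all procedures there, so these places conflict. An early-termination sample would not always help: in SAP 5.1 the Week 12 window opens at Day 63.

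**Step 4: size.** The documents give no hs-CRP effect, SD or missingness, so there is no stated figure to reproduce. The arms are 100 per active group. The step-down alphas sum correctly: 0.01 + 0.02 + 0.02 = 0.05. The following inputs are assumptions:

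- Percent change Y = 100 × (exp(Z) − 1), with Z normal and SD 0.8.
- Median change −35% on FDC and −5% on a component, 100 per arm.
- Every missing patient is off drug.
- Two-sided Wilcoxon test at 0.02 (the plan does not state sidedness).

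The Hodges-Lehmann shift is the median of all pairwise differences between arms. The observed-data version drops missing patients; the primary rule sets them to Y = 0. Over 3,000 simulated trials:

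| Missing, FDC / comparator | Observed | Primary rule | Difference (points) |
|---|---|---|---|
| 5% / 5% | −26.2 | −25.1 | 26.2 − 25.1 = 1.1 |
| 10% / 10% | −26.5 | −24.0 | 26.5 − 24.0 = 2.5 |
| 15% / 15% | −26.1 | −21.7 | 26.1 − 21.7 = 4.4 |
| 12% / 5% | −25.9 | −22.5 | 25.9 − 22.5 = 3.4 |

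At 3% in both arms the difference is about 0.5 point.

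Power, observed data against primary rule, was 0.82 against 0.81 at 5% missing and 0.74 against 0.71 at 15%. At 12% versus 5% it was 0.79 against 0.69; repeat simulations of that case gave gaps of 8 to 10 points.

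**Step 5: other assumptions.** With log SD 0.7 to 0.9, a relative reduction of 25% to 35% and 5% to 15% missing equally in both arms, the estimate shrinks by about 1 to 6 points. Power falls by about 0 to 3 points, both against a component (100 versus 100, alpha 0.02) and against placebo (100 versus 50, alpha 0.01).

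**The case against.** The strongest reply is that SAP 5.3.2 never assigns imputation to hs-CRP. Its key secondary sentence omits hs-CRP, which has its own paragraph and method. HDL-C and TG are only summarised descriptively, so the sentence about testing other endpoints at 0.05 on observed data has no tested endpoint left to govern except hs-CRP. On that reading the table title simply follows the SAP.

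This reading is coherent and cannot be excluded from the main SAP text. It conflicts, however, with the Protocol Synopsis and with the Addendum's own description of hs-CRP as key secondary. The 0.05 sentence may also be carried over from Protocol 14.6, where HDL-C and TG were the other endpoints. Membership is therefore unresolved, and text must change under either reading.

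Four further points stand:

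- The table list belongs to a post-unblinding sensitivity addendum that excludes 81 patients. It says it repeats selected key analyses, so it is good but indirect evidence. Observed-data analysis of key secondary endpoints is also a planned sensitivity analysis in SAP 5.3.3.
- SAP 5.3.1 defers detail to programming specifications, and rank-based results can be combined over imputations. The gap is one of specification.
- A step-down procedure does not require the same missing-data method for every endpoint.
- The size is wholly assumed and small when few values are missing.

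A reader might infer that the confirmatory hs-CRP test is shown to break a clearly stated rule, or that its estimate is overstated by a known amount. The documents support neither. Figure 2 is not shown, the main table shells are not available, and calling the difference an overstatement presumes that the baseline-value rule gives the true effect.

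**Conclusion.** The point holds as an unresolved and consequential gap. Two places make hs-CRP a step-down or key secondary endpoint. The SAP's rule for sequentially tested endpoints is imputation, that rule is not operational for the chosen test, and the available table list shows observed data. With the Appendix 1 sampling exemption, an observed-data analysis would exclude mainly off-drug patients despite its full-analysis-set label.

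Under the assumptions in the working, the estimate differs by about 0.5 to 1 point at 3–5% missing and by 4 to 4.5 points at 15%. Power moves by 0 to 3 points when missingness is equal. It moves by roughly 10 points only if missingness is clearly higher on FDC (12% versus 5%), which could decide whether hs-CRP passes. These are illustrations of the gap between two rules and do not estimate bias in this trial. The co-primary LDL-C conclusions are not affected. The plan should be corrected, but the defect does not undermine the trial.

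**What to change.** 1. Name the step-down endpoints and their order in the text of SAP 5.3.2.
2. If hs-CRP is among them, apply the primary's rule to it. A missing value off drug enters the rank analysis as 0% change; a missing value on drug is imputed on the log scale.
3. Prespecify a valid way to combine the rank-based results over imputations. Rubin's rules on the Hodges-Lehmann shift and its standard error, or on the normalised rank statistic, are two options. Use the combined result in the step-down.
4. Keep the observed-data Wilcoxon analysis as the sensitivity analysis already provided for in 5.3.3.
5. If hs-CRP is not among them, say so, state that it is tested on observed data outside the controlled family, and correct the Protocol Synopsis and the Addendum.
6. Reconcile the Appendix 1 note with Protocol 10.5.5 and Appendix 1 footnote 2 on hs-CRP sampling after drug withdrawal.

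The cost is a paragraph of SAP text, a short program and, under the assumptions used here, a somewhat less favourable hs-CRP estimate.

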5.3.3 Sensitivity Analyses for Efficacy Endpoints

Sensitivity analyses will be performed for the co-primary endpoints and key secondary endpoints using:

- Treatment completer analysis set using FAS with no imputation for missing data
- Observed data from the FAS with no imputation for missing data

Figure 2: The statistical testing of the treatment comparisons

5.3.4 Subgroup Analysis for Co-primary Endpoints

The co-primary endpoints for LDL-C will be analyzed within subgroups described in section 5.2.6. The treatment and subgroup interaction will be examined by including treatment, subgroup, baseline and treatment by subgroup interaction term in the ANCOVA model for the overall population first. No imputation will be performed on missing data for subgroup analyses. In case the number of subjects within a subgroup/treatment is too small for a meaningful analysis or small cell size is causing convergence issue, the analyses may not be performed or the subgroup levels may be combined.

A forest plot of treatment effect for each of the LDL-C endpoint comparison within each subgroup will be provided.

5.3.5 Exploratory Endpoints

Percent of patients with LDL-C <70 mg/dL after Week 12 will be summarized by treatment group. Comparisons between treatment groups (FDC vs. EZE, FDC vs. BA, and FDC vs. placebo) on the proportion of patients achieving an LDL-C <70 mg/dL after 12 week treatment will be performed using Fisher's exact test or Pearson's chi-square test on observed data, i.e. the denominator will be number of patients who have LDL-C value at week 12.

Descriptive summary for plasma trough concentrations of BA and/or EZE will be provided at Weeks 4, 8, and 12 by treatment group.

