7.1. Patient Inclusion Criteria

1. Provision of written informed consent prior to any study-specific procedure;
2. Age ≥ 18 years or legal age of majority depending on regional law, whichever is greater at Week -2 (Visit S1);
3. Men and nonpregnant, nonlactating women.

Women must be either:

- Naturally postmenopausal reported by the patient and defined as:
 - ≥ 55 years and ≥ 1 year without menses, or
 - < 55 years and ≥ 1 year without menses with follicle-stimulating hormone (FSH) ≥ 40.0 IU/L;
- Surgically sterile including hysterectomy, bilateral oophorectomy, or tubal ligation or;
- Women of childbearing potential willing to use at least 1 acceptable method of birth control. The minimal requirement for adequate contraception should be functional on Day 1, continuing during the study period and for at least 30 days after the last dose of study drug. Acceptable methods of birth control include:
 - oral, implantable, injectable or topical birth control medications;
 - placement of an intrauterine device with or without hormones;
 - barrier methods including condom or occlusive cap with spermicidal foam or spermicidal jelly;
 - vasectomized male partner who is the sole partner for this patient;
 - true abstinence: When this is in line with the preferred and usual lifestyle of the patient. (Periodic abstinence [e.g., calendar, ovulation, symptothermal, postovulation methods], declaration of abstinence for the duration of a trial, and withdrawal are not acceptable methods of contraception).

Note: There are no protocol-specific birth control requirements for men with partners who are able to become pregnant.

4. Treated with maximally tolerated statin therapy at stable dose for at least 4 weeks prior to screening. Maximally tolerated statin therapy may include statin regimens other than daily dosing, such as no statin to very low doses. A patient's maximally tolerated statin therapy will be determined by the investigator using their medical judgment and local

standard of care. Available sources, including the patient's self-reported history of lipid-modifying therapy will also be considered.

5. Fasting LDL-C at Week -2 (Visit S1) while on maximally tolerated statin therapy:

- ASCVD and or HeFH: ≥ 100 mg/dL (2.6 mmol/L);
- Multiple cardiovascular risk factors: ≥ 130 mg/dL (3.4 mmol/L).

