14.7. Exploratory Endpoints

The proportion of patients achieving an LDL-C <70 mg/dL after 12-week treatment will be summarized for each treatment group and the comparison between FDC vs. EZE; FDC vs. BA, and FDC vs. placebo will be based on Chi-sq test or Fisher's exact test. No missing data imputation will be applied to this analysis.

Descriptive summary for plasma trough concentrations of BA and/or EZE will be provided at Weeks 4, 8, and 12 by treatment group.

Further details will be provided in the SAP.

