3.2.3 Exploratory Endpoints

- Percentage of patients attaining LDL-C <70 mg/dL after 12 weeks of treatment.
- Plasma trough concentrations at Weeks 4, 8, and 12 of BA (ETC 1002 and its active metabolite ESP15228) and EZE (glucuronidated EZE and unconjugated EZE) in BA 180 mg + EZE 10 mg FDC-treated arm, BA-treated arm, and/or EZE alone treated arm.

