4.3 Sample Size Justification

The sample size of 100 patients per active treatment group and 50 patients in the placebo arm (2:2:2:1) of this study (350 patients total) was selected to provide adequate power for each of the co-primary endpoint as well as the co-primary endpoint family as a whole.

5 Statistical and Analytical Plans

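### The LDL-C <70 mg/dL comparisons use an unadjusted chi-square or Fisher test with no rule for choosing between them; omitting baseline LDL-C costs a little precision on an exploratory endpoint

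*SAP*

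**What the plan says.** SAP 3.2.3 lists "Percentage of patients attaining LDL-C <70 mg/dL after 12 weeks of treatment" as an exploratory endpoint. It is the only goal-attainment endpoint in the plan. For FDC versus EZE, BA and placebo, SAP 5.3.5 states that the comparison "will be performed using Fisher's exact test or Pearson's chi-square test on observed data", and that "the denominator will be number of patients who have LDL-C value at week 12". Protocol 14.7 says the comparison "will be based on Chi-sq test or Fisher's exact test". Neither text names a covariate or a stratum, or says when one test rather than the other applies.

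The primary LDL-C analysis (SAP 5.3.1) adjusts for baseline LDL-C and the randomisation strata. Those strata are statin intensity and disease category (SAP 4.2). Protocol 7.1 sets the entry LDL-C at 100 mg/dL or more for ASCVD and/or HeFH, and at 130 mg/dL or more for multiple risk factors.

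On size, SAP 4.3 says only that the sample "was selected to provide adequate power for each of the co-primary endpoint" and for that family as a whole. No power, alpha or expected attainment rate is given for LDL-C <70 mg/dL.

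**The concern.** Percent change puts patients with different starting values on a common scale; an absolute threshold does not. A patient just above the entry limit may reach 70 mg/dL with a moderate response, while a patient at 160 mg/dL needs a very large one. Baseline LDL-C is therefore the main predictor of this endpoint. The plan adjusts for it in the percent-change analysis and leaves it out of the threshold analysis.

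Two things are at stake. The first is precision in the three attainment comparisons. The second is pre-specification: chi-square and Fisher can fall on opposite sides of 0.05, and the plan leaves the choice open until the data are seen. Which patients enter the denominator is a separate question and is not part of this point.

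**Working it through.** **1. The plan's own figure.** The 2:2:2:1 allocation of 350 gives 350 × 2/7 = 100 and 350 × 1/7 = 50, as stated. There is no power figure for attainment to reproduce.

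**2. Dependence on baseline.** The fall needed to reach 70 from baseline b is 1 − 70/b:
- b = 100: 30.0%
- b = 130: 46.2%
- b = 160: 56.3%

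As an illustration, assume a mean fall of 35% with SD 20 points. The chance of attaining is Φ((35 − needed fall)/20):
- b = 100: Φ(0.25) = 60%
- b = 130: Φ(−0.56) = 29%
- b = 160: Φ(−1.06) = 14%

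**3. Order of magnitude for chi-square.** With 100 per arm at two-sided 0.05 (assumed), power = Φ((Δ − 1.96·SE₀)/SE₁). For 20% versus 10%, SE₀ = √(0.15 × 0.85 × 2/100) = 0.0505 and SE₁ = √((0.16 + 0.09)/100) = 0.0500. Power is Φ(0.02) = 50.8%. For 30% versus 15% it is 72.2%, and for 30% versus 10% it is 94.8%.

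**4. Simulation, FDC versus a single agent (100 versus 100).** Assumptions, none of them from the documents except the arm sizes and entry limits: 60% ASCVD/HeFH; 35% on high-intensity statin, with no direct effect on outcome; baseline equal to the entry limit plus a skewed spread with SD 25-35 mg/dL; 5% missing. There were 2,000 runs per setting (Monte Carlo SE at most √(0.25/2000) = 1.1 points). The stratified column is a Cochran-Mantel-Haenszel test on the four strata. The adjusted column is an ordinary logistic likelihood-ratio test with baseline LDL-C and both strata.

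| Mean change, FDC / single agent | SD of % change | Chi-square | Fisher | Stratified | Adjusted |
|---|---|---|---|---|---|
| −35 / −20 | 15 | 93.6% | 92.0% | 94.0% | 96.0% |
| −35 / −20 | 25 | 72.4% | 68.8% | 72.4% | 75.0% |
| −30 / −20 | 15 | 58.5% | 53.4% | 58.9% | 63.8% |
| −30 / −22 | 25 | 27.4% | 23.6% | 27.3% | 28.8% |

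Across all nine settings run, the adjusted test gained about 1-5 points over chi-square and 4-10 over Fisher. The strata alone added about 0-1 point.

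A second set (FDC −33%, single agent −18% or −22%, SD 15-25, 3,000 runs) gave gains of 2.3-5.6 points over chi-square and 8.2-14.9 over Fisher. In its largest case chi-square, Fisher and adjusted power were 63.8%, 54.5% and 69.4%. Of the 14.9 points over Fisher, 63.8 − 54.5 = 9.3 come from Fisher's conservatism and 69.4 − 63.8 = 5.6 from adjustment.

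**5. FDC versus placebo (100 versus 50).** With FDC at −30% or −35% and placebo at 0%, chi-square power was already 89.0-99.8%. Placebo had no attainers in about 30-90% of runs, so the ordinary logistic odds ratio cannot be estimated there. That model showed 0-5 points over chi-square, but with sparse events (5-11% attainment, no treatment effect) it rejected in 5.9-8.0% of runs. Chi-square rejected in 4.0-4.9% and Fisher in 2.8-3.7%. Part of its apparent gain is therefore inflated type I error.

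**6. The Firth-penalised fit.** With FDC −33%, single agent −18% or −22%, SD 15-25 and 1,200 runs per setting, it gained about 1-3 points over chi-square and 6-11 over Fisher. A further set of 800 runs per setting gave 1-3 and 7-10, with almost nothing against placebo. Rejection with no treatment effect was 1.0-5.5% in the first set. In the second it was 0.8-6.6%, against 4.2-6.8% for chi-square.

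**7. The open choice of test.** In the 1,200-run set, chi-square and Fisher gave opposite verdicts at 0.05 in 4-8% of the FDC versus single-agent comparisons.

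**The case against.** The case for leaving the tests alone is substantial. The endpoint is exploratory, sits outside the co-primary and step-down testing described in the text, and has no stated alpha or power. The simple tests compare the reported proportions directly and need no model. Fisher remains valid when placebo has no attainers, where ordinary logistic regression fails. The gain over chi-square, which the plan allows, is only a few points. LDL-C lowering itself is already analysed with adjustment. All of this stands, and it is why the point is minor.

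Three stronger readings are tempting and are not supported:
- **That the simple tests bring no benefit.** They are transparent, and Fisher is robust in sparse cells.
- **That ignoring the strata is an important source of lost power.** Under these assumptions the strata alone add about 0-1 point. A strong prognostic effect of statin intensity could raise that, but the documents give no evidence of one.
- **That the different entry limits, or chance baseline imbalance, bias the comparison.** The limits follow disease category, which is a randomisation stratum. Chance imbalance is already allowed for by a valid test; chi-square rejected in about 5% of runs with no treatment effect.

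What the objection does not answer is that the choice of test is left open and that the main predictor, already collected, goes unused. The type I error problem applies to the ordinary logistic model and not to the penalised fit.

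**Conclusion.** A minor point of efficiency and pre-specification. The planned tests are valid and unbiased, and no confirmatory conclusion depends on them. For FDC versus BA or EZE, adjustment adds about 1-6 points of power over chi-square and 4-15 over Fisher, nearly all of it from baseline LDL-C. With the penalised fit recommended here, the gain over chi-square lay at the lower end, about 1-3 points. For FDC versus placebo there is little or nothing to gain.

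The direction follows from the design. The size does not: the FDC effect, the SDs, the case mix and the attainment rates are all assumed, and Protocol 4.1 itself describes the size of the combined effect on statin background as not known. The missing rule for choosing between the two tests can be read directly from the text and needs no assumption.

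**What to change.** In SAP 5.3.5, with Protocol 14.7 aligned, make the analysis for all three comparisons a Firth-penalised logistic regression on treatment, continuous baseline LDL-C and the two stratification factors. Specify the penalised fit unconditionally. A switch triggered by few attainers would need a threshold and would recreate the open choice, and the ordinary fit separates and is anti-conservative in the placebo comparison.

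Report the standardised risk difference with 95% CI, and name the method for the interval and the p-value. The standardised difference keeps the result on the scale of proportions. Keep the observed proportions with Fisher's exact test as a supportive table, which also settles the choice between Fisher and chi-square.

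The cost is a few sentences and one model; every covariate is already collected. The downside is a model-based result that is less transparent than a direct comparison of proportions. For example, the fitted placebo proportion will be slightly above zero even if no placebo patient attains the goal. The SAP addenda record that unblinding has taken place, so if this analysis were run now for this trial it would have to be labelled post hoc.
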